## 3.8.3 Device Placement & Removal, Subject Pain

The easiness of VeraCept placement and removal, as well as subject pain during the procedure, is evaluated. Assessments (with possible results) during placement are:

- Were there any difficulties with device deployment? (Yes, No)
- How easy was the device placement (as rated by clinician doing the placement)?
   (Very Easy, Easy, Neither Easy nor Harder, Hard, Very Hard)
- Device placement pain (as rated by the subject)? (No Pain, Some Pain, Painful, Moderately Painful, Very Painful)
- Did the subject require mechanical dilatation? (Yes, No)

Assessments (with possible results) during the removal:

 VeraCept removal ease? (Very Easy, Easy, Neither Easy nor Hard, Hard, Very Hard)

- VeraCept removal pain (as rated by the subject)? (No Pain, Some Pain, Painful, Moderately Painful, Very Painful)
- Device expelled? (Yes, No)

The results will be summarized categorically with number and percentages of subjects in each categorical result for all these assessments. Cumulative VeraCept safety-related removal and expulsion rates at 1-year, 2-year, and 3-year will also be presented.

## 3.8.4 Device Expel and Subject Discomfort

All enrolled subjects will record device expel and discomfort through a daily diary:

- Experienced any unusual abnormal pain or pelvic pain or cramping? (None, Cramping Only, Pelvic Pain Only, Both Cramping and Pelvic Pain)
- Rate the discomfort (None, Mild, Moderate, Severe)
- Did the VeraCept device expel? (No, Yes, Suspected)

For each category of the question's answer (e.g., "Pain", Cramping", etc., all but "None" and "No"), the total number of days with that answer will be tabulated by cycle for each subject. If a cycle has less than 28 days but at least 14 days data, missing value will be imputed by the average in the same cycle for the subject, and then rounded to nearest integer.

For example, a subject at Cycle 6 has only 20 days data, of which 3 days with "Cramping". Then the total number of "Cramping" days at this cycle for her will be estimated as:

$$3 + (3 / 20 \times (28 - 20)),$$

which will be 4 after rounding to integer.

The six-number summary statistics will be presented by cycle for each parameter (i.e., categorical answer, all but "None" and "No"). Cumulative VeraCept device expulsion rates (%) at 1-year, 2-year, and 3-year will also be presented, which will be calculated as:

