12.7 Emergency Contraception

If the subject suspects the VeraCept has expelled, she should contact the study site. Emergency contraception may be administered, according to product labelling, if the subject suspects expulsion has occurred and an act of intercourse might be unprotected, and she does not want the risk of pregnancy. If the subject is subsequently found to have an *in situ* IUD and desires to continue in the study, the cycle during which she used EC will not be included in the analysis unless the subject conceives. If the IUD is expelled, she will be exited from the study.

13. Diaries

Subjects will be instructed to complete diaries daily. Diaries are designed to collect the following information for each day of each menstrual cycle:

- Day of cycle
- Date
- Absence or presence of menstrual or other bleeding (none, spotting, normal or heavy)
- VeraCept expulsion (yes, no, suspected)
- Usage of additional birth control methods and type of birth control used
- Presence of abnormal pain or cramping
- Other medical problems
- All medications taken that day
- Frequency of intercourse
- Liner, pad and tampon usage

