## 3.4 Analysis Populations

All Screened: all subjects who signed Consent Form and screened at the study sites.

Intent To Treat (ITT): All subjects who underwent the study device placement procedure, regardless of whether the study device was successfully placed or not.

Safety: ITT subjects who had the device successfully placed.

Extension: ITT subjects who agreed to continue study device use after 12 months, up to 2 additional years for a total maximum of 3 years.

Evaluable for Pregnancy (EP): ITT subjects who had VeraCept placed successfully, and must meet both requirements 1 and 2 to be EP. Subjects must also meet either requirement 3 or requirement 4 to be EP.

1. between 18 to 35 years of age (inclusive) at enrollment

2. at least one report of pregnancy status after being enrolled

AND

3. have at least 1 cycle of diary with intercourse and without any backup contraception or emergency contraception (EC)

OR

4. have an on-treatment pregnancy, which is defined as the estimated conception date being on or after the insertion date and no more than 7 days after the VeraCept is removed or expelled.

Evaluable for Cycle Control (ECYC): ITT subjects with at least one cycle for which:

- A) a pregnancy did not occur; AND
- B) there was an assessment of bleeding in the diary data; AND
- C) the cycle has 14 or more days data.

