# Subjects with device expulsion / # Subjects still in the study by that time-point x 100.

## 3.8.5 Bleeding and Spotting

Vaginal bleeding and spotting will be recorded daily by subjects in daily diary. The total number of bleeding or spotting days for each subject at each cycle, including the missing value imputation at cycles with less than 28 days but at least 14 days data, will be calculated similarly as the above Section 3.8.4, and then summarized by 6-number statistics for ECYC population. In addition, bleeding and spotting will be summarized separately. Subjects who discontinue the study due to bleeding complaints prior to completing one 28-day cycle will be included in the bleeding analysis.

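### The SAP's diary rule scales cycles cut short by removal or expulsion up to 28 days, and ECYC criterion C contradicts the stated inclusion of women who stop early for bleeding

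*SAP*

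**What the plan says.** SAP 3.8.4 counts, per woman and per cycle, the days with each diary answer other than 'None' and 'No'. Its rule for incomplete cycles is: "If a cycle has less than 28 days but at least 14 days data, missing value will be imputed by the average" for that woman in the same cycle, rounded to an integer. The worked example has 3 cramping days in 20 days of data and gives 4. One of the diary items listed there is "Did the VeraCept device expel? (No, Yes, Suspected", so the answers 'Yes' and 'Suspected' fall under the same rule.

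SAP 3.8.5 builds the bleeding and spotting totals the same way, "including the missing value imputation at cycles with less than 28 days but at least 14 days data", and summarises them for the ECYC population. It adds: "Subjects who discontinue the study due to bleeding complaints prior to completing one 28-day cycle will be included in the bleeding analysis".

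ECYC, in SAP 3.4, requires at least one cycle meeting three conditions joined by AND. The third is that "the cycle has 14 or more days data". The list of outputs in SAP 5.2 gives ECYC as the population for Table 14.3.8 (bleeding and spotting days by cycle).

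On participation after expulsion, Protocol 12.7 says: "If the IUD is expelled, she will be exited from the study".

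**The concern.** A cycle can hold fewer than 28 days of data for two different reasons. The woman may have skipped diary entries while using the device, and filling those days from the rest of her cycle is a reasonable convention. Or the device may have been removed or expelled, so that the remaining days of device use do not exist. The rule treats both alike. For the Pearl Index the SAP does make the distinction: section 3.7.1 credits a partial last cycle only with its days at risk divided by 28. The diary rule has no counterpart.

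Truncated cycles are built into the design. Expulsion ends participation, early removals fall anywhere in a cycle, and the Week 52 ± 2 window allows on-schedule removal before Cycle 13 is complete. Women who stop early because of pain, bleeding or expulsion are among those affected, and their last cycles are informative about tolerability.

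The ECYC conflict bears on the same women from the other side. Someone who stops for bleeding on day 10 of Cycle 1 is promised a place in the bleeding analysis but does not qualify for the population on which the table is run.

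**Working it through.** **Inputs.** From SAP 3.8.4: x = days with a given answer, n = days of data in the cycle (14 to 27), target 28. Cycle length is 28 days (SAP 3.8.1). The exit window is Week 52 ± 2 (Protocol Table 1), with target Day 364 (SAP 3.8.6).

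**Formula.** x + (x/n)(28 − n) = 28x/n, rounded to the nearest integer.

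**The plan's own example.** x = 3, n = 20: 3 + (3/20)(8) = 4.2, which rounds to 4. This reproduces the SAP.

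**The same formula for a complete diary that stops on day n because the device is gone.** Entries are the tabulated days:

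| n | 28/n | x = 1 | x = 3 | x = 5 | x = 7 |
|---|---|---|---|---|---|
| 14 | 2.00 | 2 | 6 | 10 | 14 |
| 16 | 1.75 | 2 | 5 | 9 | 12 |
| 18 | 1.56 | 2 | 5 | 8 | 11 |
| 19 | 1.47 | 1 | 4 | 7 | 10 |
| 21 | 1.33 | 1 | 4 | 7 | 9 |
| 24 | 1.17 | 1 | 4 | 6 | 8 |
| 27 | 1.04 | 1 | 3 | 5 | 7 |

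As a hypothetical larger case, ten bleeding days in 14 give 28 × 10/14 = 20. Ten of those days fall after removal.

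**Expulsion item.** With x = 1, 28/n is at least 1.5 for n = 14 to 18 (2.00, 1.87, 1.75, 1.65, 1.56) and rounds to 2. At n = 19 it is 1.47 and rounds to 1, as it does up to n = 27. If the expulsion day were uniform over the cycle and the diary complete up to it (both assumed), 5/28 = 18% of expulsions would be tabulated as two days.

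**Exit within the window.** Cycle 13 runs from Day 337 (12 × 28 + 1) to Day 364. Removal on Day 350, the first day of the window, leaves 350 − 336 = 14 days, so the factor is 2.0. Removal on Day 363 leaves 27 days. A woman who keeps the device after Week 52 differs: if her diary ends at that visit, the rest of Cycle 13 is unrecorded but the device is in place.

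**Effect on the summary statistics.** Assume a 5-day menses starting uniformly in 28 days (wrapping round), with the first 14 days observed. Of the 28 starting days, 10 give 5 observed days, 10 give none, and two each give 1, 2, 3 and 4. The mean is (50 + 20)/28 = 2.5. The mean square is (250 + 60)/28 = 11.07, so the SD is √(11.07 − 6.25) = 2.2. Doubling gives an imputed mean of 5.0, SD 4.4 and range 0 to 10. As an estimate of a full 28-day cycle the mean is unbiased, but the SD, minimum and maximum are distorted. As a count of days with the device it is twice the true 2.5.

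**ECYC.** Take a woman who stops for bleeding on day 10 of Cycle 1. SAP 3.8.5 includes her. SAP 3.4 criterion C fails, because her only cycle has at most 10 days of data. Table 14.3.8 is run on ECYC, so she is not in it. The precedence clause in SAP 3.1.3 ranks specific sections above the general conventions of that section; it does not rank 3.8.5 above 3.4. Protocol 20.7 makes the same inclusion statement, and the ECYC definition in Protocol 20.1 has no 14-day condition, so the conflict enters with the SAP.

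**The case against.** A reader might infer that the plan counts expulsions twice. It does not. SAP 3.8.3 summarises expulsion by number and percentage of subjects, and the cumulative rate at the end of 3.8.4 has subjects in its numerator. Only the by-cycle count of diary days is affected. Whether that count is displayed is uncertain: the title of Table 14.3.7 names only discomfort, and the table shells are a separate document.

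Nor does the rule set post-removal days to symptomatic. It fills them at the woman's own observed rate, which can be defended as a standardised per-cycle rate; unscaled short cycles would look mild beside full ones. That point stands and is a reason to show truncated cycles apart, with their device days, rather than mix them unscaled with full cycles.

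The term 'missing value' could be read as diary gaps only. The SAP states no such limit, however, and its formula fixes the target at 28.

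'Suspected' is not a terminal answer: under Protocol 12.7 a woman found to have the device in situ may continue, so such days can recur. It needs separate handling from 'Yes'.

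On ECYC, 3.8.5 can be read as a specific exception to criterion C. That is probably the intent, but the SAP does not say so and gives no rule for tabulating such a woman's days. It would also go too far to say that early stoppers are always either extrapolated or dropped. A woman with another qualifying cycle remains in ECYC, and the SAP does not say that her shorter cycles are excluded.

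Finally, these are descriptive summaries in a study the SAP calls exploratory, and tolerability in early stoppers also appears in the discontinuation reasons and in the tables of adverse events leading to discontinuation.

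**Conclusion.** The point holds for the by-cycle diary summaries. In cycles cut short with 14 to 27 days of data, bleeding, spotting, cramping and pain days are extrapolated to days without a device, by a factor between 28/27 = 1.04 and 2.0. One expulsion 'Yes' day becomes two in the by-cycle day count at 14 to 18 days of data. Separately, criterion C and the inclusion sentence in 3.8.5 contradict each other for a woman whose only cycle has fewer than 14 days.

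This rests on reading the formula as written, with its fixed 28. The documents do not say how many cycles are truncated at 14 to 27 days, so the shift in any by-cycle mean cannot be estimated, and a general bias in the means cannot be claimed. The effect is confined to descriptive secondary tolerability summaries. The Pearl Index and the subject-level and cumulative expulsion rates are not touched. It should be corrected, but it does not threaten the main conclusion of the study.

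**What to change.** In SAP 3.8.4 and 3.8.5:

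- Impute only unrecorded diary days while the device was in place. Replace 28 by D, the device-in-place days in that cycle, giving x + (x/n)(D − n) = xD/n. A complete diary in a truncated cycle has D = n and nothing is added: 3 in 14 stays 3 instead of becoming 6. The SAP's own example still gives 4 when its eight days are true gaps (D = 28).
- Show cycles cut short by removal, expulsion or exit in a separate row, with observed symptom days and device days.
- Take the expulsion item out of the imputation. Report confirmed expulsion once per woman by date, and 'Suspected' days as observed.

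In SAP 3.4, exempt women who discontinue for bleeding in Cycle 1 from ECYC criterion C, and state that their observed days are used.

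No new data are needed; removal dates are already used in SAP 3.2. The cost is more than wording. Table 1 of the protocol schedules diaries only to Week 52, and SAP 3.1.2 describes the 1-year outputs as already created and final. Tables 14.3.7 and 14.3.8 would therefore have to be re-run for Year 1, with an added row for truncated cycles.

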# Subjects with device expulsion / # Subjects still in the study by that time-point x 100.

## 3.8.5 Bleeding and Spotting

Vaginal bleeding and spotting will be recorded daily by subjects in daily diary. The total number of bleeding or spotting days for each subject at each cycle, including the missing value imputation at cycles with less than 28 days but at least 14 days data, will be calculated similarly as the above Section 3.8.4, and then summarized by 6-number statistics for ECYC population. In addition, bleeding and spotting will be summarized separately. Subjects who discontinue the study due to bleeding complaints prior to completing one 28-day cycle will be included in the bleeding analysis.

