VeraCept was successfully placed in all enrolled subjects with no peri-procedural adverse events and without the use of anesthetics, pre-medication or mechanical dilatation. The VeraCept Intrauterine Copper Contraceptive, in this initial experience, satisfied the objectives of providing a safe, easy to place, conformable low-dose copper contraceptive that is highly tolerated.

In the Phase II Confirmation portion of the Pilot Study, the Subject Continuation Rate is 90% at 10 months, with only 2% expulsion rate and 3% discontinuation for tolerability. The remaining 5% discontinued due to other reasons (e.g. the desire to get pregnant or inability to comply with study follow-up requirements.)

Comparative Study of the VeraCept Intrauterine Copper Contraceptive

Subsequent to the Pilot Study, a 2:1 randomized, subject-blinded Comparative Study of the VeraCept Intrauterine Copper Contraceptive vs. the TCu380 IUD is being conducted in a population of parous women enrolled at a single site. The interim results to date demonstrate that VeraCept has achieved equivalent performance in terms of safety and effectiveness as compared to the predicate TCu380 IUD, i.e. no serious adverse events and no intrauterine or ectopic pregnancies in either group, while achieving clinically and statistically significant improvements in subject-related outcomes such as improved tolerability, reduced expulsions and reduced pain-at-insertion.

VeraCept was successfully placed in 99.5% of all subjects to whom the study device was randomly assigned, with no peri-procedural adverse events, and without the use of anesthetics, pre-medication or mechanical dilatation. No new or unanticipated adverse events were introduced. Statistically significant improvements (95% CI) in Subject Continuation Rate, Tolerability, Study Device Expulsion and Pain at Insertion were all demonstrated when compared to the control intrauterine device.

In this experience to date, VeraCept satisfied the objectives of providing a safe, easy to place, conformable low-dose intrauterine copper contraceptive without sacrificing safety or effectiveness. Study completion to 12 months and, subsequently, a larger multicenter study is warranted.

This Phase II Clinical Study is designed to evaluate the effectiveness, study device placement, safety, and tolerability of VeraCept to support a larger, Phase III clinical study.

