4.4 VeraCept Dosage Modification

All subjects will receive the same VeraCept dosage of 175mm² exposed copper surface area. No Study Devices will be replaced if an expulsion or removal occurs.

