20.7 Safety And Other Outcome Measures

All safety and other outcome measures will be analyzed using the ITT/Safety Population unless noted otherwise. Confidence intervals will be provided to support interpretation of the observed safety rates.

VeraCept Characteristics

Study device ease of placement and placement success will be summarized. Cumulative study device expulsion rates will be summarized

Adverse Events

The number and percentage of subjects with each adverse event and serious adverse event will be presented in a table by MedDRA system-organ class and preferred term. Summaries will also be presented by relationship to the VeraCept placement or removal procedure and the severity of the adverse event. All adverse events will be summarized with special attention to those events that may be related to an intrauterine contraceptive, including:

- Anemia
- Back pain
- Dysmenorrhea
- Dyspareunia
- Ectopic pregnancy
- Embedment, which in some cases may require surgical removal

- Expulsion, partial or complete
- Intrauterine pregnancy
- Leukorrhea
- Medical diathermy
- Menstrual flow, prolonged / vaginal bleeding
- Menstrual spotting
- Movement of study device during MRI
- Pain and cramping
- Pelvic infection, which can lead to Fallopian tubal damage leading to ectopic pregnancy or infertility, hysterectomy, sepsis and rarely death
- Pelvic Inflammatory Disease (PID), which can lead to tubal damage leading to ectopic pregnancy or infertility, or infrequently can necessitate hysterectomy, or cause death.
- Uterine perforation, which may lead to pre-operative imaging followed by laparscopy or laparotomy to remove the IUD from the peritoneal cavity
- Septic abortion
- Uticarial allergic skin reaction
- Vaginitis
- Vasovagal reaction at the time of placement, including fainting.

VeraCept Safety-Related Removal Rates and Expulsion Rates

Cumulative VeraCept safety-related removal rates and expulsion rates at each year will be summarized.

Bleeding and Spotting Patterns

Vaginal bleeding and spotting will be recorded daily by the subject in her diary. The ECYC population will be used for the bleeding and spotting summaries. The number of bleeding or spotting days will be summarized for each cycle. In addition, bleeding and spotting will be summarized separately. Subjects who discontinue the study due to bleeding complaints prior to completing one 28-day cycle will be included in the bleeding analysis.

Other Safety Assessments

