## 3.1.3 Analysis Conventions

This section details general policies to be used for the statistical analyses. Departures from these general policies may be given in the specific detailed sections of this statistical analysis plan. When this situation occurs, the rules set forth in the specific section take precedence over the general policies. The following policies will be applied to all data presentations and analyses.

- Summary statistics will consist of the number and percentage of responses in each category for discrete (categorical) variables, and the number of non-missing observations (n), mean, median, standard deviation (SD), minimum, and maximum (abbreviated as 6-number summary statistics) for continuous variables.
- All mean values will be formatted to one more decimal places than the measured value, and standard deviation values will be formatted to two more decimal places than the measured value. For median values, they will be kept the same decimal place as the measured values if that is doable without losing accuracy; otherwise, they will be formatted to one more decimal place than the measured values.
- All percentages will be rounded to one decimal place. The number and percentage
  of categorical responses will be presented in the form XX (XX.X), where the
  percentage is in the parentheses. The denominator for percentage calculations will
  be either the number of non-missing observations (n) when this number is shown, or
  the total sample size of the relevant sample size for tables of adverse events, medical
  histories, or other tables where this number of non-missing observations (n) is not
  presented.
- All listings will be sorted for presentation in the order of site identifier, subject identifier, and date of procedure or event.
- When necessary for analysis purposes, partial dates will be completed (i.e., turned into complete dates) using the most conservative approach.
- All analysis and summary tables will have the population sample size in the column heading.
- Baseline is defined as the last data point before the placement of study product.
- Calculating change from baseline to a visit will be done as follows: Change from Baseline = Observed value at the visit – Baseline value.
- Subjects who have only baseline (without any post-baseline measurements) for a
  parameter at a visit, or only have post-baseline value for a parameter at a visit, will be

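### The yearly cumulative expulsion rates divide by women still in the study, so once any device is expelled they come out too high, and they rise further as women leave for other reasons

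*SAP*

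**What the plan says.** Protocol 20.7 makes the commitment: "Cumulative VeraCept safety-related removal rates and expulsion rates at each year will be summarized". It gives no formula. SAP 3.8.3 repeats the promise for 1, 2 and 3 years, also without a denominator. SAP 3.8.4 supplies the only calculation. It announces that "Cumulative VeraCept device expulsion rates (%) at 1-year, 2-year, and 3-year will also be presented" and defines them as "Subjects with device expulsion / # Subjects still in the study by that time-point x 100".

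Two protocol rules determine who is in that denominator. Section 12.7: "If the IUD is expelled, she will be exited from the study". Section 4.4: "No Study Devices will be replaced if an expulsion or removal occurs".

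The general percentage rules in SAP 3.1.3 do not override the formula, because in a conflict "the rules set forth in the specific section take precedence over the general policies". The Kaplan-Meier analyses in SAP 3.7 and the figures listed in SAP 5.2 concern pregnancy only.

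**The concern.** A cumulative rate should be the share of women who started at risk and had the event by a given time, with allowance for those whose follow-up ended early. Here the numerator accumulates every expulsion since placement, while the denominator counts only the women left at the end. Expelled women are in the first and not in the second. Women who had the device removed, were lost, or chose not to go beyond 12 months also leave the denominator, although they were at risk of expulsion earlier. The figure therefore rises with unrelated drop-out even when no further device is expelled, and it has no ceiling at 100%.

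These are the yearly figures a reader would set beside other IUD data or the pilot study's own rate. Years 2 and 3 are most exposed, because continuing past 12 months is optional (SAP 2.3).

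**Working it through.** The documents give no expulsion figure for this trial, so there is nothing to reproduce. The check compares the SAP formula with standard estimators on the same data.

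**Notation.** N = women with the device placed, E = women with an expulsion by the time-point, R = women still in the study then. Because expelled women exit, N ≥ E + R.

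**Direction.**
- SAP formula: E/R.
- Crude rate: E/N.
- One minus Kaplan-Meier (1−KM) equals E/N if all expulsions come before any other exit, and E/(E+R) if all other exits come first. Other orders fall between.
- The cumulative incidence with other removals as competing events is never above 1−KM.
- For E ≥ 1: E/N ≤ 1−KM ≤ E/(E+R) < E/R.

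The SAP figure is thus above all the others whenever a device has been expelled. With no expulsions, all are zero.

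**Figures found in the documents.** The Protocol's Introduction reports 90% continuation at 10 months in the pilot "with only 2% expulsion rate and 3% discontinuation for tolerability", and a further 5% leaving for other reasons. These add up on the full base: 100 − 2 − 3 − 5 = 90. Then:
- crude: 2.0%
- SAP formula: 2/90 = 2.22%
- 1−KM at most: 2/92 = 2.17%

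The Introduction also gives first-year discontinuation of 4–15% for copper IUDs. Keeping the 2% expulsion and counting it within that discontinuation, the SAP formula gives 2/96 = 2.08% to 2/85 = 2.35%.

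**Assumed range for lower retention.** N = 250 is the planned maximum. E = 5 is the pilot's 2%. The retention levels are assumptions and are not tied to a particular year.

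| Retained | R | SAP E/R | Crude E/N | 1−KM at most, E/(E+R) | 1−KM, random order of exits |
|---|---|---|---|---|---|
| 60% | 150 | 5/150 = 3.3% | 2.0% | 5/155 = 3.2% | 2.5% |
| 40% | 100 | 5/100 = 5.0% | 2.0% | 5/105 = 4.8% | 3.0% |
| 20% | 50 | 5/50 = 10.0% | 2.0% | 5/55 = 9.1% | 3.9% |

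The last column is the mean of 4,000 random orderings. The approximation 1 − (R/N)^(E/(N−R)) agrees; for R = 100 it is 1 − 0.4^(5/150) = 3.0%. The number of expulsions is the same in all three rows; only drop-out differs.

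With E = 10 the SAP formula gives 6.7%, 10.0% and 20.0%, against a crude 4.0% and 1−KM of at most 6.3%, 9.1% and 16.7%.

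**Simulation.** Eight scenarios of 400 trials each, N = 250. The assumed yearly hazards over years 1/2/3 were 2/1/1% or 5/2/2% for expulsion and 8/8/8% or 13/15/15% for other removal, with 0% or 30% of women leaving at 52 weeks. The ratio of mean SAP figure to mean 1−KM was:

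| Year | SAP ÷ (1−KM) |
|---|---|
| 1 | 1.07–1.13 |
| 2 | 1.14–1.71 |
| 3 | 1.21–1.85 |

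The SAP figure was the largest in all 9,583 simulated trial-years with at least one expulsion.

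**The case against.** The strongest reply is that little depends on this figure. Expulsion rate is not among the endpoints in SAP 2.4, the study is single-arm and described as exploratory, and the review committee in Protocol 20.8 is triggered by pregnancies. The error runs against the device. SAP 3.8.3 also plans an overall expelled yes/no percentage, and if expulsions are recorded as adverse events, the year-by-year tables in SAP 3.8.2 will show them over the Safety population. This stands as a limit on the harm. It does not make the yearly cumulative rates right: the yes/no percentage is not a rate by year, and the adverse event tables take no account of follow-up.

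A second reply is that SAP 3.8.4 does not define who is still in the study. The exclusion of expelled women comes from the protocol, and a woman who expels just before a time-point may not yet have exited. That is fair, and the term is also unclear for women who exit within the Week 52 ± 2 window. But keeping all expelled women in the denominator gives E/(E+R), which is still never below 1−KM. In the 20% row it moves 10.0% only to 9.1%, against about 3.9% under random ordering. Under that ordering most of the excess comes from the other leavers, so adding the expelled women back is not a sufficient repair.

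Third, the large differences rest on assumed retention. This also stands: the first-year figures available in the documents give a small effect, and the number of women continuing past 12 months is not stated.

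**Conclusion.** The formula is wrong as written and should be fixed. The direction is certain on the documents' own rules: given at least one expulsion, it exceeds the crude rate, 1−KM and the competing-risk cumulative incidence computed on the same data. That is a comparison of estimators, not with a known true rate.

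The size is small at year 1: about 2.2% against 2.0% on the pilot percentages, and 7–13% above 1−KM in relative terms in the simulations. It may be substantial at years 2 and 3, 14–85% above in relative terms across the simulated scenarios. Those later figures depend on the assumed expulsion and exit rates. The damage is confined to the yearly cumulative expulsion rates; the primary analysis is not affected.

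**What to change.** Replace the formula in SAP 3.8.4. Estimate cumulative expulsion at 1, 2 and 3 years from time since placement in the SAP Safety population, "ITT subjects who had the device successfully placed", with 95% confidence intervals. Name one estimator in advance:

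- 1−KM, censored at removal for another reason or at last contact; or
- cumulative incidence, with other removals as competing events.

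The two answer different questions, so the choice should be stated, together with how removals by choice at 52 weeks are treated. If a crude rate is shown as well, divide by all successfully placed women. State the method and denominator for the cumulative safety-related removal rates in SAP 3.8.3 too, since none is given.

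The cost is a change of SAP wording and a short programming change. SAP 3.7.1 already uses placement, removal and expulsion dates, and SAP 3.7.2 already uses Kaplan-Meier with censoring. SAP 3.1.2 says the 1-year outputs have been produced, under a Version 1.00 SAP that is not among the documents. If they used this formula, the 1-year expulsion rate should be recomputed and re-issued.
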